12.4.3 Handling of missing values/censoring/discontinuations

Participants with unknown or missing BOR as per RECIST 1.1 will be counted as failures. If there is no baseline tumor assessment, all post-baseline overall lesion responses are expected to be 'Unknown'. If no valid post-baseline tumor assessments are available, the best overall response must be "Unknown" unless progression is reported. For the computation of ORR, these participants will be included in the FAS and will be counted as 'failures'.

Only tumor assessments performed on or before the start of a new antineoplastic treatment other than study drug(s) will be considered in the assessment of BOR.

12.4.4 Sensitivity and Supportive analyses

Supportive and sensitivity analyses will be conducted to support the primary objective, if appropriate, and the details of these analyses will be defined in the SAP.

12.5 Analysis of secondary endpoints

The secondary objectives are:

- To assess the efficacy of each treatment arm with respect to Duration of response (DOR), Time to response (TTR), Progression Free Survival (PFS), and Clinical benefit rate (CBR) per investigator's assessment according to RECIST v1.1
- To assess Overall Survival for each treatment arm

- To characterize the safety profile of each treatment arm
- To characterize the pharmacokinetics (PK) of LAG525, spartalizumab and carboplatin in the three investigated combinations
- To assess immunogenicity of LAG525 and spartalizumab in the three investigated combinations

12.5.1 Efficacy and/or Pharmacodynamic endpoint(s)

Clinical benefit rate (CBR) is defined as the proportion of participants with a best overall response of complete response (CR) or partial response (PR) or an overall lesion response of stable disease (SD), lasting for a duration of at least 24 weeks. CR, PR and SD are defined as per local review according to RECIST 1.1 (see Section 16.3 Appendix 3 for details). CBR will be evaluated according to RECIST 1.1 (see Section 16.3 Appendix 3 for details).

CBR based on RECIST 1.1 will be calculated based on the FAS and according to the ITT principle. CBR and its two-sided exact binomial 95% confidence interval Clopper CJ and Pearson 1934 will be presented by treatment group.

Time to response (TTR) is defined as the time from the date of randomization to the first documented response of either complete response (CR) or partial response (PR), which must be subsequently confirmed (i.e., the start date of response, not the date when response was confirmed).

TTR will be evaluated according to RECIST 1.1 (see Section 16.3 Appendix 3 for details).

All participants in the FAS will be included in TTR calculations. Participants without a confirmed CR or PR will be censored at the study-maximum follow-up time (i.e., LPLV-FPFV) for participants with a PFS event (i.e., disease progression or death due to any cause), or at the date of the last adequate tumor assessment for participants without a PFS event. TTR will be listed and summarized by treatment group. TTR will be analyzed in the FAS population according to the treatment groups assigned at randomization. The TTR distribution will be estimated using the Kaplan-Meier method, and the Kaplan-Meier curves, medians and 95% confidence intervals of the medians will be presented for each treatment group only if a sufficient number of responses is observed.

Duration of response (DOR) only applies to participants whose best overall response is complete response (CR) or partial response (PR) based on tumor response data per local review. DOR will be evaluated according to RECIST 1.1 (see Section 16.3 Appendix 3 for details).

The start date is the date of first documented response of CR or PR (i.e., the start date of response, not the date when response was confirmed), and the end date is defined as the date of the first documented progression or death due to underlying cancer. Participants continuing without progression or death due to underlying cancer will be censored at the date of their last adequate tumor assessment. DOR based on RECIST 1.1 will be listed and summarized by treatment group for all participants in the FAS with confirmed BOR of CR or PR. DoR will be analyzed in the FAS population according to the treatment groups assigned at randomization. The DoR distribution will be estimated using the Kaplan-Meier method, and the Kaplan-Meier curves, medians and 95% confidence intervals of the medians will be presented for each treatment group only if a sufficient number of responses is observed.

Progression-Free Survival (PFS) is defined as time from date of randomization to the date of event defined as the first documented progression or death due to any cause. PFS will be assessed via local review according to RECIST 1.1 (see Section 16.3 Appendix 3 for further details). PFS will be censored if no PFS event is observed before the earliest of (i) the analysis cut-off date, and (ii) the date when a new anti-neoplastic therapy is started. The censoring date will be the date of the last adequate tumor assessment prior to cut-off/start of new anti-neoplastic therapy.

PFS will be analyzed in the FAS population according to the treatment groups. The PFS distribution will be estimated using the Kaplan-Meier method, and the Kaplan-Meier curves, medians and 95% confidence intervals of the medians will be presented for each treatment group.

Overall Survival (OS) is defined as the time from date of randomization to date of death due to any cause. If a participant is not known to have died, then OS will be censored at the latest date the participant was known to be alive (on or before the cut-off date). OS will be analyzed in the FAS population according to the treatment groups. The OS distribution will be estimated using the Kaplan-Meier method, and the Kaplan-Meier curves, medians and 95% confidence intervals of the medians will be presented for each treatment group.

12.5.2 Safety endpoints

For all safety analyses, the safety set will be used. All listings and tables will be presented by treatment group.

Safety summaries (tables, figures) will include only data from the on-treatment period with the exception of baseline data which will also be summarized where appropriate (e.g., change from baseline summaries). In addition, a separate summary for death including on treatment and post treatment deaths will be provided. In particular, summary tables for adverse events (AEs) will summarize only on-treatment events, with a start date during the on-treatment period (treatment-emergent AEs).

The on-treatment period lasts from the date of first administration of study treatment to 30 days after the date of the last actual administration of any study treatment.

The overall observation period will be divided into three mutually exclusive segments:

- Pre-treatment period: from day of participant's informed consent to the day before first dose of study medication
- On-treatment period: from day of first dose of study medication to 30 days after last dose of study medication
- Post-treatment period: starting at day 31 after last dose of study medication.

If dates are incomplete in a way that clear assignment to pre-, on-, or post-treatment period cannot be made, then the respective data will be assigned to the on-treatment period. Additional details to address incomplete AE and/or dosing dates will be addressed in the SAP.

Adverse events

Summary tables for adverse events (AEs) will include only AEs that started or worsened during the on-treatment period, the *treatment-emergent* AEs.

Additional summaries will be displayed to report all AEs, AEs related to study treatment, all SAEs and SAEs related to study treatment collected up to 150 days after last administration of LAG525/spartalizumab or up to 30 days after the last dose of carboplatin whichever comes last.

The incidence of treatment-emergent adverse events (new or worsening from baseline) will be summarized by system organ class and or preferred term, severity (based on CTCAE grades), type of adverse event, relation to study treatment.

Serious adverse events, non-serious adverse events and adverse events of special interest (AESI) during the on-treatment period will be tabulated.

All deaths (on-treatment, up to 150 days after last administration of LAG525/spartalizumab or up to 30 days after the last dose of carboplatin whichever comes last, and post-treatment) will be summarized.

All AEs, deaths and serious adverse events (including those from the pre and post-treatment periods) will be listed and those collected during the pre-treatment and post-treatment period will be flagged.

Vital signs

Data on vital signs will be tabulated based on notable vital sign values. All vital signs data will be listed by treatment group, participant and visit/time, notable values will be flagged.

12-lead ECG

12-lead ECGs including PR, QRS, QT and QTcF will be obtained for each participant during the study. ECG data will be read and interpreted centrally.

All ECG data will be listed by treatment group, participant and visit/time, abnormalities will be flagged. Categorical analysis of QT/QTc interval data based on the number of participants meeting or exceeding predefined limits in terms of absolute QT/QTc intervals or changes from baseline will be presented.

Clinical laboratory evaluations

All laboratory data will be listed by treatment group, participant, and visit/time.

Grading of laboratory values will be assigned programmatically as per NCI Common Terminology Criteria for Adverse Events (CTCAE) version 5.0. The calculation of CTCAE grades will be based on the observed laboratory values only, clinical assessments will not be taken into account.

CTCAE Grade 0 will be assigned for all non-missing values not graded as 1 or higher. Grade 5 will not be used.

For laboratory tests where grades are not defined by CTCAE version 5.0, results will be categorized as low/normal/high based on laboratory normal ranges.

The following listings/summaries will be generated separately for hematology and biochemistry tests:

• Listing of all laboratory data with values flagged to show the corresponding CTCAE version 5.0 grades if applicable and the classifications relative to the laboratory normal ranges

For laboratory tests where grades are defined by CTCAE version 5.0

- Worst post-baseline CTCAE grade (regardless of the baseline status). Each participant will be counted only once for the worst grade observed post-baseline.
- Shift tables using CTCAE version 5.0 grades to compare baseline to the worst ontreatment value

For laboratory tests where grades are not defined by CTCAE version 5.0,

Shift tables using the low/normal/high/ (low and high) classification to compare baseline to the worst on-treatment value.

Other safety evaluations

Other safety data (e.g., cardiac imaging) will be summarized or listed as appropriate.

12.5.3 **Pharmacokinetics**

The respective PAS for each study drug will be used in the pharmacokinetic data analysis.

Drug concentration values below the lower limit of quantitation (LLOO) will be displayed in listings as zero with a flag and handled as zero in the calculations for mean, CV for mean, standard deviation, minimum, median, maximum, but handled as missing for the calculation of the geometric means and their CV.

Descriptive statistics (n, m (number of non-zero concentrations), mean, CV%, SD, median, geometric mean, geometric CV%, minimum and maximum) for spartalizumab, LAG525 and carboplatin concentrations will be presented at each scheduled timepoint and visit by treatment group.

All spartalizumab, LAG525 and carboplatin concentration data will be displayed graphically and by treatment group and visit.

PK parameters may be calculated using the PK sampling in cycle 1 and cycle 3, as appropriate. The descriptive statistics (n, mean, CV%, standard deviation (SD), median, geometric mean, geometric CV%, minimum and maximum) will be presented for all PK parameters for spartalizumab, LAG525 and carboplatin by treatment group for both cycle 1 and cycle 3 defined in Table 12-1 except Tmax, where only n, median, minimum and maximum will be presented.

Table 12-1	Non-compartmental pharmacokinetic parameters for spartalizumab, LAG525 and carboplatin
AUClast	The AUC from time zero to the last measurable concentration sampling time (tlast) (mass x time x volume-1)
AUCtau	The AUC calculated to the end of a dosing interval (tau) at steady-state (amount x time x volume-1)
Cmin or Ctrough	The minimum observed plasma or serum drug concentration (mass x volume-1)
Cmax	The maximum (peak) observed plasma, blood, serum, or other body fluid drug concentration after single dose administration (mass x volume-1)
Tmax	The time to reach maximum (peak) plasma, blood, serum, or other body fluid drug concentration after single dose administration (time)

[figure not shown]
12.5.3.1 Data handling principles

Missing values for any PK parameters or concentrations will not be imputed and will be treated as missing.

Below the limit of quantitation (BLQ) values will be set to zero by the Bioanalyst, and will be displayed in the listings as zero and flagged. BLQ values will be treated as missing for the calculation of the geometric means and geometric CV%.

[figure not shown]
12.5.4 Immunogenicity

Immunogenicity will be characterized descriptively by tabulating anti-drug antibodies (ADA) prevalence at baseline and ADA incidence on-treatment. Additional details will be specified in the SAP.

Novartis Amended Protocol Version 04 (Clean)	Confidential	Page 128 of 185 Protocol No. CLAG525B2101

12.7 Interim analyses

No formal interim analysis is planned for this trial. The primary analysis of the study data will be reported in the primary CSR based on all participants' data up to the time when all participants have been followed for efficacy (tumor assessments) for at least 24 weeks or discontinued tumor assessments for any reason prior to 24 weeks. Any additional data (e.g., DoR, OS, safety) for participants continuing to receive study treatment past the data cutoff date for the primary CSR, as allowed by the protocol, will be reported in the Final analysis on completion of the study.

12.8 Sample size calculation

12.8.1 Primary endpoint(s)

The sample size calculation is based on the primary variable ORR considering the statistical model, hypothesis and method of analysis detailed in Section 12.4.2. Proof of preliminary efficacy (PPE) for each drug combination (study arm) will be declared if both of the following conditions are met:

- the mean of the posterior distribution of ORR is at least 35% and
- the posterior probability that the ORR is $\geq 25\%$ is at least 0.9

Approximately 32 participants were planned to be enrolled in each arm for a total of approximately 96 participants. In a given arm of 32 participants, the type-I error rate is 8% while the probability of declaring proof of preliminary efficacy (PPE) is at least 80% for ORR ≥ 45% (Table 12-2). With protocol amendment 3, enrollment to treatment Arm 1 (LAG525 + spartalizumab) was prematurely closed. Therefore, approximately 84 participants will be enrolled (approximately 20 participants in Arm 1, and 32 participants per arm for Arms 2 and 3).

Table 12-2 Operating characteristics with 32 participants in each arm

True ORR	Probability of declaring PPE in each arm (12 or more responders)	Probability of missing PPE (11 or less responders) in each arm
25 %	0.079	0.921
30 %	0.228	0.772
35 %	0.448	0.552
40%	0.675	0.325
45 %	0.847	0.153

13 Ethical considerations and administrative procedures

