Variable (or endpoint)	The variable (or endpoint) to be obtained for each participant that is required to address the clinical question. The specification of the variable might include whether the participant experiences an intercurrent event.
Withdrawal of study Consent (WoC)	Withdrawal of consent from the study occurs only when a participant does not want to participate in the study any longer, and does not allow any further collection of personal data

Amendment 4 (15-Feb-2021)

At the time of amendment 4, 20 participants have been randomized to treatment Arm 1, 34 participants have been randomized to treatment Arm 2, and 34 participants have been randomized to treatment Arm 3. Of the 88 randomized participants, 85 participants have discontinued the study treatment. Three participants are still receiving treatment in Arm 2 (LAG525 + spartalizumab + carboplatin), 3 participants are in safety follow-up (of which one is still in efficacy follow-up) and 12 are in survival follow-up.

Amendment rationale

The primary efficacy analysis was performed with a data cut-off date of 27-Feb-2020. None of the three treatment arms met the proof of preliminary efficacy (PPE) criteria of a mean of the posterior distribution of $ORR \ge 35\%$ and a posterior probability of $(ORR \ge 25\%) > 90\%$. No new safety signals were identified for any of the treatment arms.

Based on these results and together with an increasingly crowded treatment landscape in metastatic TNBC, Novartis decided to not further develop LAG525 in TNBC. This decision is not due to safety concerns.

The main purpose of this amendment is to: 1) define the duration of the follow-up period and 2) clarify the trial discontinuation rules for participants who are still ongoing in the trial as to whether they are eligible for a Post Trial Access (PTA) program i.e. rollover protocol or a post study drug supply (PSDS).

The following modifications were incorporated:

- The survival follow-up period will be removed and participants who are currently in survival follow-up can discontinue from the study with approval of amendment 4.
- The post treatment follow-up period will be limited to the safety follow-up period of 150 days after the last dose of LAG525 and/or spartalizumab (whichever was stopped last). If carboplatin was stopped more than 150 days after LAG525 and/or spartalizumab, the participant can be discontinued 30 days after the last dose of carboplatin.

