With protocol amendment 3, enrollment to treatment Arm 1 (LAG525 + spartalizumab) was prematurely closed. Participant data from Arm 1 will still contribute to the efficacy and safety objectives of the trial as per the analysis defined in this section.

The primary analysis of the study data will be reported in the primary CSR based on all participants' data up to the time when all participants have been followed for efficacy (tumor assessments) for at least 24 weeks or discontinued tumor assessments for any reason prior to 24 weeks. Any additional data (e.g., DoR, OS, safety) for participants continuing to receive study treatment past the data cut-off date for the primary CSR, as allowed by the protocol, will be reported in the Final analysis on completion of the study.

Any data analysis carried out independently by the investigator should be submitted to Novartis before publication or presentation.

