16.2 Appendix 2: Statistical considerations

The primary endpoint is the overall response rate (ORR). The analysis of the primary endpoint, which is Bayesian, uses a binomial sampling and a Beta prior distribution.

Based on clinical discussions and available literature, the null value for the ORR was set to 25%. Moreover, a minimum ORR improvement of 10% was considered necessary to justify further development (see Section 12.4.2 for information on published data available to help elicit the 25% and 35% targets).

The two criteria to assess the proof of preliminary efficacy (PPE) in each treatment group are thus:

- Clinical relevance: posterior mean ≥ 35%
- Bayesian statistical significance: $pr(ORR \ge 25\% \mid data) \ge 0.90$

The first criterion is met if the posterior mean ORR is at least 35% which is the minimum ORR of clinical interest. The second criterion provides reasonable evidence that the posterior ORR is better than the null value of 25%. Both criteria need to be met by at least one treatment group in order to meet the primary objective of the study.

Each analysis by treatment group is performed separately using a Beta-binomial model as follows:

Let us assume that y_i out of n_i patients have a response as per ORR in treatment group i (either LAG525 + spartalizumab, LAG525 + spartalizumab + carboplatin or LAG525 + spartalizumab + carboplatin).

The likelihood function is $y_i \sim Bin(n_i, p_i)$ where p_i denotes the ORR for treatment group i.

Assume p_i follows a beta prior distribution: $[p_i] \sim \text{Beta}(a_i, b_i)$, where $a_i > 0$, $b_i > 0$

The posterior distribution of p_i is therefore: $[p_i | y_i] \sim \text{Beta}(a_i + y_i, b_i + n_i - y_i)$

A minimally informative prior with unimodal Beta(0.35/(1-0.35),1) distribution is used. The prior parameters are chosen so that the prior mean for ORR is equal to 35%. This ensures that the clinical relevance criterion is met, if the observed ORR is exactly equal to 35%.

With the two criteria stated above the minimally required sample size is 32.

To better understand the design, operating characteristics for various true ORR were assessed using simulations as follows:

- Generate 100,000 trials with ORR results (yes / no) for n_i participants per treatment group, where the ORR follows a binomial distribution $y_i \sim Bin(n_i, p_i)$.
- Evaluate for each of these simulated trials whether the PPE criteria are met.

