5.4 Statistical models

5.4.1 Primary analysis

Analysis of Binary Data

Dual-criterion based Proof of Concept designs

The two criteria to assess the proof of preliminary efficacy (PPE) in each treatment group are thus:

- Clinical relevance: posterior mean $\geq 35\%$
- Bayesian statistical significance: $\text{pr}(\text{ORR} \geq 25\% \mid \text{data}) \geq 0.90$

Let p_i denote the ORR for treatment group i and which follows a beta prior distribution Beta $[a, b]$, where $a > 0$, $b > 0$. Let y_i out of n_i subjects be responders. Therefore, the posterior distribution of p_i is Beta $(a + y_i, b + n_i - y_i)$ [Spiegelhalter et al. 2004].

A minimally informative unimodal Beta prior [Neuenschwander et al. 2008] Beta $[0.35/(1-0.35), 1]$ will be used. The parameters were chosen so that the mean of the prior distribution is equal to 0.35, which ensures that the clinical relevance criterion is met, if the observed ORR is exactly equal to 35%.

The efficacy criteria will be assessed based on the actual number of subjects enrolled in the study. For example, if the total number of subjects is 32 in a given treatment group, the first efficacy criterion requires that at least 12 subjects are responders. In that case, the posterior distribution is Beta $(0.35/(1-0.35)+12, 1+32-12)$ and the posterior probability $\text{pr}(\text{ORR} \geq 25\% | \text{data}) = 0.939$.

For further details, see [Appendix 2 of the study protocol](#).

Confidence interval for response rate

Responses will be summarized in terms of percentage rates with 95% confidence intervals using exact binomial confidence interval (implemented using SAS procedure FREQ with EXACT statement for one-way table [[Clopper and Pearson 1934](#)]).

Analysis of time to events Data

Kaplan-Meier estimates

An estimate of the survival function in each treatment group will be constructed using Kaplan-Meier (product-limit) method as implemented in PROC LIFETEST with METHOD=KM option. The PROC LIFETEST statement will use the option CONFTYPE=LOGLOG.

Median survival for each treatment group will be obtained along with 95% confidence intervals calculated from PROC LIFETEST output using the method of [[Brookmeyer and Crowley 1982](#)]. Kaplan-Meier estimates of the survival function with 95% confidence intervals at specific time points will be summarized. The standard error of the Kaplan-Meier estimate will be calculated using Greenwood's formula [[Collett 1994](#)].

Treatment of ties

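### Arm 1 stays under the proof-of-preliminary-efficacy (PPE) rule with about 20 participants, but the plan gives operating characteristics only for larger arms, and SAP 3.1 still plans about 32 per arm.

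*Protocol*

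**What the plan says.** Protocol 12.8.1 applies the PPE rule to every study arm. Two conditions must both hold: a posterior mean ORR of at least 35%, and a posterior probability of at least 0.9 that the ORR is 25% or more. The section then gives the design's error rates. The sentence begins "In a given arm of 32 participants, the type-I error rate is 8" (per cent) and goes on to claim at least 80% probability of PPE once the true ORR reaches 45%. Table 12-2 is headed "Operating characteristics with 32 participants in each arm" and puts the bar at 12 responders. The same paragraph then reduces the enrolment target: "Therefore, approximately 84 participants will be enrolled (approximately 20 participants in Arm 1, and 32 participants per arm for Arms 2 and 3".

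Arm 1 is not dropped from the analysis. The opening of Protocol Section 12 says: "Participant data from Arm 1 will still contribute to the efficacy and safety objectives of the trial". SAP 5.4.1 says: "The efficacy criteria will be assessed based on the actual number of subjects enrolled in the study". The amendment 4 summary records that "20 participants have been randomized to treatment Arm 1", with 34 in each of Arms 2 and 3, and reports a PPE result for all three arms.

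Protocol Appendix 2 (16.2) tabulates operating characteristics for 32, 36 and 40 participants and nothing smaller. It also says: "With the two criteria stated above the minimally required sample size is 32".

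The SAP introduction states that it is based on protocol v04. Even so, SAP 3.1 still plans about 32 subjects in each arm (about 96 in total), repeats the n=32 error rates and table, and does not mention the reduced Arm 1. SAP 1.1 also gives about 96 subjects randomized 1:1:1, then describes the closure of Arm 1 without changing that number. SAP Section 4 lists no change to the protocol-specified analyses.

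**The concern.** A decision rule is applied to an arm of 20 when neither document states the responder threshold or the error rates at that size. A reader of SAP 3.1 would attach the n=32 figures to Arm 1, because the SAP still plans 32 there. A reader of Protocol 12.8.1 finds only the n=32 table and has to notice that it leaves Arm 1 out.

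At stake is how much weight the Arm 1 result can bear. Judged against the printed table, a missed PPE has about a 15% chance of occurring when the true ORR is 45%. If the rule is less sensitive at n=20, the reported Arm 1 result is weaker evidence against activity than a reader would suppose. The false-positive rate also differs from the printed one.

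**Working it through.** **Inputs**
- Prior: Beta(0.35/0.65, 1) = Beta(0.5385, 1) (Protocol 16.2, SAP 5.4.1).
- Criteria: posterior mean ≥ 0.35 and Pr(ORR ≥ 0.25 | data) ≥ 0.90 (Protocol 12.8.1 and 16.2).
- Arm sizes: 32 (Table 12-2 and SAP Table 3-1); 20, 34 and 34 randomized (amendment 4 summary).

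**Formulas**
- With y responders out of n, the posterior is Beta(0.5385 + y, 1 + n − y), with mean (0.5385 + y)/(1.5385 + n).
- The PPE threshold r is the smallest y that meets both criteria.
- The probability of PPE at true rate p is P(Bin(n, p) ≥ r).

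**Step 1. Reproduce the plan at n = 32**
- y = 11: mean 11.5385/33.5385 = 0.344; Pr(ORR ≥ 25%) = 0.878. Fails.
- y = 12: mean 12.5385/33.5385 = 0.374; Pr(ORR ≥ 25%) = 0.9385. Passes, and agrees with the 0.939 in SAP 5.4.1.
- With r = 12, the exact tails at ORR 25/30/35/40/45% are 0.0804, 0.2283, 0.4485, 0.6767 and 0.8487. The tables print 0.079, 0.228, 0.448, 0.675 and 0.847. All agree within 0.002, which is consistent with the 100,000-trial simulation described in 16.2.

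**Step 2. The same rule at n = 20**
- y = 7: mean 7.5385/21.5385 = 0.350; Pr(ORR ≥ 25%) = 0.835. The mean criterion is met, the probability criterion is not.
- y = 8: mean 8.5385/21.5385 = 0.396; Pr(ORR ≥ 25%) = 0.926. Both are met, so r = 8 (8/20 = 40%, against 12/32 = 37.5%).

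| True ORR | Printed, n = 32 (≥ 12) | Exact, n = 20 (≥ 8) |
|---|---|---|
| 25% | 0.079 | 0.102 |
| 30% | 0.228 | 0.228 |
| 35% | 0.448 | 0.399 |
| 40% | 0.675 | 0.584 |
| 45% | 0.847 | 0.748 |

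The chance of missing PPE at ORR 45% is 1 − 0.748 = 25.2%, against 1 − 0.847 = 15.3% printed.

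**Step 3. Why 20 behaves differently**
For n from 10 to 79, I compared the threshold from the mean criterion alone with the threshold from both criteria. They differ at n = 10 to 20, 22, 25, 28 and 31, and agree at every n from 32 up. This is consistent with Appendix 2 calling 32 the minimum. At 20 the probability criterion sets the bar; the mean criterion alone would need only 7 responders.

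**Step 4. Sensitivity to an approximate size of 20**
- n = 19 (r = 8): 0.683 at ORR 45%, 0.078 at ORR 25%.
- n = 21 (r = 8): 0.803 at ORR 45%, 0.130 at ORR 25%.

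**Step 5. Arms 2 and 3 at the 34 randomized**
- y = 11: mean 11.5385/35.5385 = 0.325. Fails.
- y = 12: mean 12.5385/35.5385 = 0.353; Pr(ORR ≥ 25%) = 0.906. Passes, so r = 12.
- Probability of PPE: 0.119 at ORR 25%, 0.906 at ORR 45%.

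**The case against.** The best defence is that the protocol prints no wrong number. Its error-rate sentence is limited to an arm of 32, the table heading says 32, both reproduce, and the cut to about 20 is disclosed in the same paragraph. That stands for the protocol, where the defect is an omission. It does not rescue SAP 3.1, which still plans 32 for Arm 1.

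A second defence is that SAP 5.4.1 already evaluates the rule at the actual number enrolled, and that ORR with exact interval and posterior is already planned by arm. This also stands: the rule itself is applied properly at 20. What is missing is any statement of how it performs there.

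A third is timing. Enrolment is over, the primary analysis used a February 2020 cut-off, and the current SAP was amended for a close-out report with no inferential analysis. The remedy can therefore only affect description and interpretation.

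Several stronger readings are tempting but unsupported:
- **That the Arm 1 result would change.** No responder count for Arm 1 appears in the documents, so 7 of 20 is purely illustrative.
- **That an observed 35% is the PPE bar and Arm 1 was held to a harsher one.** Appendix 2 ties 35% to the clinical-relevance criterion only and requires both criteria. Even at n=32 the bar is 37.5%.
- **That 80% is reached only at 32.** It is also reached at n=21 and n=34, for example.
- **That closing Arm 1 contradicts the absence of a formal interim analysis.** The documents describe a review by the sponsor and steering committee. That review makes the n=20 figures nominal, but it does not conflict with the statement that no formal interim analysis was planned.

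**Conclusion.** The point holds as a misstatement of sample size in SAP 3.1 and a gap in Protocol 12.8.1. The n=32 operating characteristics do not describe Arm 1. At 20 participants the probability of PPE at ORR 45% is 9.9 points below the printed value (0.748 against 0.847) and under the 80% stated for an arm of 32. The type-I error is about 10% instead of 8%. At ORR 30% the two sizes agree.

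The figures rest on the protocol's prior, both criteria, exact binomial sampling and exactly 20 in Arm 1. One participant either way moves the 45% figure to between 0.683 and 0.803. They are nominal, because enrolment was stopped after a review showing more discontinuations for progressive disease in Arm 1, and that selection is not modelled.

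The conclusion is limited to how the Arm 1 PPE result should be read. It does not bear on whether that result, or the decision to stop development in this indication, was right.

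**What to change.** 1. Correct SAP 3.1 and SAP 1.1 to the amendment 3 sizes: about 20 in Arm 1, 32 in each of Arms 2 and 3, about 84 in total.
2. In Protocol 12.8.1 and SAP 3.1, state that the n=32 table and the 80% statement do not apply to Arm 1.
3. Add an n=20 row: 8 or more responders; PPE probability 0.102 / 0.228 / 0.399 / 0.584 / 0.748 at ORR 25 / 30 / 35 / 40 / 45%. Mark it nominal because the arm was closed after review of progression-related discontinuations.
4. In the study report, quote error rates at the actual arm sizes for all three arms. For Arms 2 and 3 at n=34 (12 or more responders) these are 0.119 at ORR 25% and 0.906 at ORR 45%. Keeping the n=32 rates there would understate the type-I error.
5. Present the Arm 1 result through its ORR, posterior and exact interval, as already planned, without attaching n=32 error rates to it.

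The cost is some wording and one table row. No further enrolment or new analysis is needed. The stated sensitivity for Arm 1, and the stated type-I error for all three arms, become less favourable.
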